UAVG Dutch Act on Implementation of the General Data Protection Regulation;

in Dutch: Uitvoeringswet AVG

VAT Ventilatory Anaerobic Threshold

WMO Medical Research Involving Human Subjects Act; in Dutch: Wet Medisch-

wetenschappelijk Onderzoek met Mensen

SUMMARY

Rationale: An aneurysm of the abdominal aorta (AAA) is a potentially life-threatening condition. Growth control and preventive surgery are important. It is proven safe to train patients with an AAA aiming to enhance aerobic fitness and improve surgical outcomes. Hypothesis: Training of patients awaiting their surgery for an AAA improves preoperative aerobic fitness. However, not all patients will improve their aerobic fitness following these training sessions.

Objective: The main objective is to separate patients who benefit from training from patients who do not benefit from training in terms of the change in CoF. The secondary objective is to study if training leads to change of aerobic fitness (CoF) in AAA patients after supervised training with a patient-specific training program. Feasibility of the study will be evaluated as well.

Study design: This is a single-arm intervention study. Patients, elected for AAA surgery, are invited to participate in this study. After inclusion, patients' socio-economic and personal characteristics are collected in a questionnaire, as well as their comorbidities (frailty-score, daily activities, ASA-score, dietary habits). All included patients will train at home under the responsibility of the principal investigator and the remote supervision of a specialist in sports medicine and a physical therapist, using home monitoring by means of the Luscii app. **Study population:** Patients with an indication for elective AAA surgery (endovascular and open surgery). Excluded are patients with AAA and an urgent (within less than 3 weeks) repair of the aneurysm and ruptured or symptomatic patients. Patients with genetic connective tissue disorders (e.g., Marfan) and patients unable to train will be excluded as well

Intervention: Patients who signed informed consent (IC) for this study must fill out a questionnaire, with the assistance of a research nurse and perform a cardiopulmonary exercise test (CPET). Patients rejected from training will be excluded. This is evaluated by the cardiologist and the specialist in sports medicine. Subjects fit for training start with home monitoring (pulse oximeter and sphygmomanometer) under the remote supervision of a physical therapist. All patients will be supported with dietary substitution to avoid a catabolic condition preceding the operation. Before and after three-to-nine-week (on average six weeks) training program, subjects are evaluated by a specialist in sports medicine, to evaluate CoF with a CPET. All patients will be followed until three months postoperative.

Main study parameters/endpoints: The main endpoint is the analysis of patients who improve from training compared to patients who do not improve from training. Secondary endpoints are:

- change in oxygen uptake (VO2) at the ventilatory anaerobic threshold (VAT) after the training program.
- program feasibility (recruitment rate, adherence, completion rate, drop-out rate, attrition rate, and adverse events).
- the (preliminary) effect of the program on other cardiopulmonary exercise testing (CPET) values, e.g., VO2 at peak exercise, oxygen uptake efficiency slope, and response profiles, as well as strength improvement.
- Postoperative events will be compared in relation to the subgroup analysis of patients benefiting from training or not.

Nature and extent of the burden and risks associated with participation, benefit and group relatedness: Patients will be asked to fill out a questionnaire with a research nurse and visit a cardiologist and a specialist in sports medicine preceding their training. During their three-to-nine weeks preoperative period, patients will be asked to train. This will be tiresome but rewarding; we expect to accomplish an increase in physical fitness. The elderly seem capable of performing home monitoring. The extra energy and proteins necessary for the training will be substituted with extra FortiFit®. These substitutes help patients to get into an anabolic condition, preoperatively. Apart from the extra consultations and the training the patient will not undergo extra laboratory tests other than necessary for regular AAA surgery. The risks are minor, for it has been proven safe to train patients indicated for elective AAA surgery in advance. Still, we wish to monitor at home, and training is prohibited outside office hours. This enables the research team to educate patients in health-related issues (heart rate recovery) and virtual hospital contact, earlier described as a Surgery School. Furthermore, it is expected that patients are encouraged by the virtual feedback. Risk benefit analysis: the risks of causing harm are small, because patients will be physically evaluated before training starts and will be monitored for safety throughout the program. The benefits may be substantial for improving surgical outcome, patients have been taught to train in their living context, and home monitoring improves extramural communication and ease hospital capacity issues.

INTRODUCTION AND RATIONALE

Abdominal aneurysms (AAAs) affect a range of 1.9-18.5% of men and less than a quarter in women (1). In recent years the mortality rate is declining (2-4) and thirty-day mortality rate of an elective repair remains at 2-3% and higher for women (5).

Cardiopulmonary evaluation assesses operative risks in patients undergoing AAA surgery (6, 7). The decrease of operative mortality was mainly due to technical innovations (4), but no attention has been paid to fitness of patients. Preoperative exercise training improves aerobic fitness (e.g., the oxygen uptake (VO₂) at the ventilatory anaerobic threshold (VAT)) (7).

Several trials have established exercise training to be safe in people with AAA and training does not seem to influence aneurysm growth (8-11). Professional supervision (e.g., physical therapy and in-hospital aerobic exercise training) is expensive. Home-based monitoring of exercising patients with AAA is less expensive, and device handling by patients has been positively evaluated before (12).

This study is designed to investigate whether patients with AAA can improve their preoperative aerobic fitness during 3- to 9-week (6 weeks on average) training program. It is primarily designed to evaluate which patients benefit most from this program, based on three outcome measures: initial fitness (CPET), BMI and age. Home training will be performed with home-monitoring and weekly support by a physical therapist.

A successful six-week training program is a true investment, and some patients will not be able to benefit from it. At this point we are unable to select patients who will benefit most. Improvement of aerobic fitness probably depends on a combination of patient specific factors, e.g., age and sex, comorbidity, aerobic fitness at the start of the training, dietary habits, comorbidity, SES, frailty index, ASA-score, physical strength, and the available social support. Training specific factors play a role as well, such as the number of prescribed training sessions, intensity, and the duration. This study is designed to select patients who will benefit most from training, based upon their initial fitness, their BMI and their age. Patients with an AAA and an indication for operative repair were often male smokers, with high blood pressure, and lipid profiles (1). Depending on their diligence, recruitment rate, adherence, completion, drop-out, and attrition rate, will be important. These rates will be evaluated in relation to SES and other characteristics. During training, patients will be supported with dietary substitutes, in order to maintain an anabolic condition (13). Due to the training at home, the Luscii app (CE-certificate 0476) enables patients to ask questions and this might stimulate them to start training, under the suggestion to be observed by the call center.

OBJECTIVES

Primary Objective: To compare patient characteristics between patients with clear improvement (more than 1.5 ml/kg/min improvement in the VO2 at VAT) after a three-to-nine-week training program, with patient characteristics of those who do not improve after training We aim to identify three factors that predict responsiveness to improve preoperative aerobic fitness following the training program.

Secondary objective: To evaluate the preliminary effectiveness of an, on average, six-week home-monitored training program, in patients with AAA scheduled for elective AAA-repair to improve the preoperative VO2 at the ventilatory anaerobic threshold (VAT).

Other Secondary Objective(s):

Other secondary aims are to evaluate the feasibility of this three-to-nine-week homemonitored training program. A fall-out of some patients is expected because physical exercise requires perseverance and endeavor. This feasibility is evaluated with:

- recruitment rate (how many patients will consent to participate in relation to the patients refusing participation).
- adherence rate (how many patients will endure participation in relation to the patients who give up participation, a.k.a. dropout rate) (Appendix 1).
- completion rate (how many patients will complete participation in relation to the number of patients ending participation).
- drop-out rate (how many patients will drop out of participation in relation to the number of patients completing participation).
- Attrition rate (how many patients will ask if a transfer to another treatment facility is possible, a.k.a. churn rate).

Additionally, the individual (preliminary) effect of prehabilitation on other CPET variables will be evaluated, such as VO₂ at peak exercise (VO_{2peak}) and the oxygen uptake efficiency slope, individual response profiles on the progression in aerobic fitness, improvement of the steep ramp test throughout the program. (Appendix 2).

The postoperative course in patients after AAA repair will be described as well, by collecting data on the surgical intervention and postoperative outcomes (e.g., hospital length of stay (HLOS), number of complications, mortality rate, readmission rate).

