Following the explanation, patients have their intake with a physical therapist. The patients able to perform training, will be prescribed a personalized exercise program and will be followed by a local physical therapist. This includes a training scheme for exercises at home (Appendix 2). They will be asked to train at home and once a week at the physical therapist, check their vital sings with the pulse oximeter and de SMM, and communicate these vital

Version number: 4

signs with the Luscii app to a call center Altide. In case of previously set limitations, this call center will contact the hospital (Appendix 3).

Home-monitored training

All eligible patients will participate in a three-to-nine-week (average of six weeks), partly supervised, home-monitored training program prior to elective AAA-repair. The second CPET measurement is planned after the training program. Training frequency during the prehabilitation will be five sessions per week including a weekly evaluation by the physical therapist. Training sessions at home are prepared and should be able to be performed without extra adjuncts (see below). Before and after home-monitored training sessions without a physical therapist, subjects communicate oxygen saturation, heartrate, blood pressure, number of steps (nS), and number of smoked cigarettes through the Luscii app. According to these measurements, automatic advises will be given through the app (Appendix 3).

To evaluate a difference after the average of six weeks, subjects visit the specialist in sports medicine a second time to perform a CPET. Depending on the performance of patients in relation to the improvement in this second CPET, a subdivision of an improved and a stable (not improved) group will be made. It is expected that improved patients will show an increase of their VO2 at VAT of 1,5 ml/kg/min or more.

Three months after surgery, monitoring is complete, and preoperative patient characteristics of the groups will be compared.

Home-monitored exercises

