2.4. Sample size calculation

A multivariable regression analysis will be performed to identify important risk factors, such as a low fitness at the beginning of the training, a low or high BMI ($20 \ge BMI \ge 31$), and a low or high age ($50y \ge age \ge 90y$)(18). With the rule of thumb requiring 10 subjects per variable, and a chance of improvement of 50% (3 variables (fitness t= 0, BMI, and age) x 10 subjects x 0,5= 60); 60 patients will be required to include. Inclusion of one hundred patients will be necessary to perform a multivariable regression analysis with three variables, assuming an exclusion rate of 20%, and a drop-out rate of 20%. Three small sample, randomized controlled trials showed higher VO2 at VAT after 3, 6, or

9 weeks of training in gastroenterological cancer patients, patients with AAA, and rectal cancer patients, respectively: of 10,1%; 18%; or 29% (Table 1)(11, 19, 20).

Version number: 4

Study	Inclusion	n	Wks	% Impro-	VO2	SD	95%CI	VO2	SD	95%CI	ΔVO2
				vement	t=0			t=1			
Berkel(19)	GE-patients	28	3	10,1	9,6	1,2	9,1 - 10,1	10,5	1,36	10 - 11,1	0,9
Barakat(11)	AAA patients	20	6	18	12,2		10,5 - 14,9	14,4		12,3 - 15,4	2,2
Loughney(20)	Rectal CA	17	9	29	11,6	3,4	9,9 - 13,3	15	4,2	12,7 - 17,3	3,4
	total	65			•						

Table 1. Three randomized controlled trials evaluating fitness after training. Wks= weeks, SD= standard deviation, GE= gastroenterological, AAA= abdominal aorta aneurysm, and CA= cancer.

These patients reached an improvement ranging from 0.9 ml/kg/min up to 3.4 ml/kg/min (assumed mean 1.5 ml/kg/min). When subdividing the group of patients into a group with increased fitness (> 1.5 ml/kg/min) and a group without increased fitness (≤ 1.5 ml/kg/min), a dichotomous outcome is reached.

The multivariable analysis will be performed with other patient specific characteristics, as well, such as comorbidities. Modifiable factors will be analyzed as well, such as dietary habits, social economic status, frailty score, and other information collected in the questionnaires.

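### The per-kg responder cut-off can create or distort a BMI association, and the protocol does not say which body weight divides the second CPET

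*Protocol*

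**What the plan says.** The Primary Objective defines clear improvement as "more than 1.5 ml/kg/min improvement in the VO2 at VAT". Section 2.4 makes this the binary outcome by dividing patients into "a group with increased fitness (> 1.5 ml/kg/min) and a group without increased fitness (≤ 1.5 ml/kg/min), a dichotomous outcome is reached". Section 1 repeats the threshold, with a slightly different boundary, as "an increase of their VO2 at VAT of 1,5 ml/kg/min or more".

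The Introduction says the study asks who benefits most "based on three outcome measures: initial fitness (CPET), BMI and age". Section 2.4 sizes the study on the same set: "3 variables (fitness t= 0, BMI, and age". It gives 20 and 31 as the limits for low and high BMI.

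On nutrition, the Summary says of the supplements: "These substitutes help patients to get into an anabolic condition, preoperatively". The Introduction says "patients will be supported with dietary substitutes, in order to maintain an anabolic condition (13". The Intervention paragraph of the Summary speaks of avoiding a catabolic state. No expected change in body weight is given.

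The protocol does not say whether the second CPET is divided by baseline weight or by weight measured again. Absolute VO2 at VAT (ml/min) is not named among the secondary CPET variables or in section 8.

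**The concern.** BMI is weight over height squared, and the outcome has weight in its denominator, so a predictor and the unit of the outcome share a component. A fixed per-kg threshold asks a heavier patient for a larger rise in oxygen uptake. If training adds a similar number of ml/min at every body size, the regression would show heavier patients responding less often although their absolute response is the same.

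The denominator can also move between the two tests. If current weight is used each time, a patient who loses weight can cross the threshold with less gain in oxygen uptake, and one who gains weight can miss it with more.

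This matters because the study is meant to select patients for training, with BMI as one of three named criteria. A BMI association that comes from the denominator could be read as evidence about who should be offered the programme. The protocol has no analysis that would tell the two apart.

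**Working it through.** **Inputs from the protocol.** Cut-off 1.5 ml/kg/min (Primary Objective, section 2.4); BMI limits 20 and 31 (section 2.4); baseline VO2 at VAT 12.2 ml/kg/min (Table 1, AAA row).

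**Assumptions, not in the protocol.** Height 1.75 m; BMI mean 27.5, SD 4.5; mean gain 130 ml/min with SD 100, 130 or 160; baseline SD 2.5 ml/kg/min; age mean 73, SD 7; a patient of 80 kg for the weight examples; weight change with mean 0% and SD 2%.

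**The plan's own figure.** 3 predictors × 10 / 0.5 = 60, and 60 / (1 − 0.40) = 100. Both reproduce, and nothing below alters them.

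**1. Absolute gain needed.** Gain = 1.5 × BMI × height².
- BMI 20: 1.5 × 20 × 1.75² = 1.5 × 61.25 kg = 92 ml/min
- BMI 31: 1.5 × 31 × 1.75² = 1.5 × 94.94 kg = 142 ml/min
- Ratio 31 / 20 = 1.55, i.e. 55% more at any height.

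**2. Effect on the BMI odds ratio.** Large simulated samples, with a logistic model for a gain per kg above 1.5 and with baseline VO2 at VAT per kg, BMI and age as predictors. Weight is held constant.

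| How the ml/min gain relates to body size | Adjusted odds ratio per 5 BMI units |
|---|---|
| Unrelated | 0.69 to 0.80 |
| Half common, half scaling with weight | 0.83 to 0.90 |
| Proportional to weight | about 1.0 |
| Proportional to baseline VO2 | about 1.0 |

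The ranges run over the three gain SDs. Adjusting for baseline fitness per kg does not remove the effect in the first two rows.

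**3. Weight change, if current weight is used.** Measured change = (12.2 + g) / (1 + p) − 12.2, where g is the gain per kg of baseline weight and p the fractional weight change.
- g = 0, p = +2%: 12.2 / 1.02 − 12.2 = −0.24 ml/kg/min
- g = 1.5, p = +2%: 13.7 / 1.02 − 12.2 = 1.23
- g = 1.5, p = −2%: 13.7 / 0.98 − 12.2 = 1.78
- Weight loss that alone makes a responder: 1 − 12.2 / 13.7 = 10.9%

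At 80 kg, the absolute gain that just reaches the cut-off is 13.7 × 80 − 12.2 × 80 = 120 ml/min at stable weight. It is 13.7 × 82 − 976 = 147 ml/min after +2 kg and 13.7 × 78 − 976 = 93 ml/min after −2 kg.

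**4. Patients who change group.** With weight change of mean 0% and SD 2%, and a gain SD of 100 to 160 ml/min at 80 kg (1.25 to 2.0 ml/kg/min), 4 to 7% fall on the other side of the cut-off. With a gain SD of 1 to 3 ml/kg/min the range is 3 to 9%.

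**The case against.** A reader might infer that a BMI effect is built into who counts as improved, so that the regression will report that heavy patients do not benefit. The documents do not support that. It requires the ml/min gain to be unrelated to body size, which the protocol neither states nor implies. The programme points partly the other way: home exercise is largely walking, stair climbing and rising from a chair, where a heavier patient moves more mass, and Appendix 2 sets interval load as a fraction of the patient's own peak. If gains scale with weight or baseline VO2, the adjusted BMI effect vanishes.

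The planned size also limits the claim. With 60 patients and half improved, the standard error of the log odds ratio per 5 units is about 5 / √(60 × 0.25 × 4.5²) = 0.287. An odds ratio of 0.69 to 0.80 would then reach p < 0.05 with only about 25% to 12% power. If low and high BMI are coded together as one risk category, opposite distortions would partly cancel.

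A reader might also infer that the supplements raise weight. The protocol speaks variously of reaching an anabolic state, maintaining it and avoiding catabolism, while training spends energy. The direction is unknown.

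The scale is that of the trials in Table 1, from which the cut-off comes, and ml/min is not the truer scale: if gains follow body mass, it favours heavy patients. The denominator could also be left to an analysis plan.

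These points remove the strong reading. What stands is that the protocol itself fixes a per-kg endpoint beside a weight-based predictor, leaves the weight at the second test open, and plans nothing to show whether a BMI finding depends on the scale.

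**Conclusion.** The point holds in a limited form. The per-kg cut-off can create or distort a BMI association. It does not necessarily do so: the adjusted odds ratio per 5 BMI units lies anywhere from about 0.7 to 1.0, depending on how the absolute gain relates to body size, which the protocol gives no data to settle.

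The weight-change part is conditional on current weight being used at each CPET. It is then modest, about 4 to 7% of patients under the assumed 2% SD, mostly those near the cut-off. It disappears with baseline weight.

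The use of ml/kg/min is not a mistake, and the sample size is unaffected. All sizes rest on the assumed height, BMI, gain and weight-change distributions listed above. This is a cheap improvement to the definition of the primary outcome, not a flaw that invalidates the study.

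**What to change.** - In the Primary Objective and section 2.4, state that the change in VO2 at VAT is computed with baseline body weight in the denominator at both CPETs. Keep the 1.5 ml/kg/min cut-off.
- In section 8.1, add one sensitivity model: a linear regression with the continuous change in absolute VO2 at VAT (ml/min) as outcome, and baseline absolute VO2 at VAT, BMI and age as predictors. A continuous outcome avoids having to invent an ml/min cut-off.
- Report the BMI result on both scales. If they disagree, say that the BMI finding depends on the scale, and suppress neither.

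Baseline weight settles only the weight-change part; the second model and the two-scale report deal with BMI. The cost is a sentence in each place and one extra model. VO2 in ml/min and baseline weight already underlie ml/kg/min and BMI, so no visit or measurement is added. The small downside is slightly less comparability with the published per-kg gains in Table 1.

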Four times a week subjects perform exercises at home, preceded and followed by communication of preset parameters through the Luscii app. These exercises include stair-climbing and sit-to-stand exercises (high-intensity), as well as outdoor cycling, outdoor walking, and outdoor running (moderate intensity). The combination will be assembled in close collaboration between the physical therapist and the specialist in sports medicine, under the responsibility of the principal investigator. Through registration and monitoring activities by the patient, the physical therapist will be able to advise activities performed at home. The physical therapist will discuss these findings with the patient on a weekly base and adjust the scheme in relation to physical improvement.

Once a week subjects perform a steep ramp test performance to estimate aerobic fitness, under the supervision of the physical therapist. This test is used to optimize training intensity of the interval and endurance training sessions, as well as to monitor progression.

Nutritional supplementation

Version number: 4

To support muscle protein synthesis, participants will be provided with protein supplementation immediately following exercise and (approximately 30 minutes) before sleep, providing a standard dosage of 30 g of a high-quality (whey and casein) protein that contains at least 10 g of essential amino acids, of which 2-3 g Leucine. Since vitamin D is associated with muscle mass and muscle strength. It will be supplemented daily according to guidelines of the Health Council of the Netherlands (10 μ g for woman aged 50-69 years, for men <70 years and women <50 years with colored skin and/or little sun exposure, and 20 μ g for women and men aged 70 years or older)(14, 15). To prevent patients from having a deficiency of vitamins and minerals below recommended doses before surgery, all other vitamins and minerals are supplied in a multivitamin/mineral supplement containing 50% of the recommended daily allowance (13).

[figure not shown]

Figure 1: flow chart (https://app.diagrams.net) concerning the references of patients. FT= physical therapy, CPET= cardiopulmonary exercise test, HLOS= hospital length of stay.

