The treatment consists of a daily training at home during weekdays, according to the instructions of a physical therapist, under the supervision of a specialist in sports medicine, and responsibility of the principal investigator. This home training is initiated after heartrate (HR), blood pressure (RR) and oxygenation (SpO2) measurement. Smoking people will be asked to communicate the number of cigarettes smoked each day.

Besides the home training, subjects will be asked to attend a weekly training at the physical therapist. Again, HR, RR and pO2 will be communicated through the home monitoring device.

Before starting the three-to-nine-week training, a cardiopulmonary exercise test (CPET) at the specialist in sports medicine is performed to objectively assess VO₂ at the VAT and other variables related to aerobic fitness. The CPET will be an extra burden to our subjects. After 3-9 weeks of training, this CPET will be repeated to monitor improvement or deterioration of the subjects.

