Appendix 2; Exercise scheme at home and with the physical therapist

Maandag	Dinsdag	Woensdag	Donderdag	Vrijdag
20 minuten	20 minuten	Fysiotherapeut	20 minuten	20 minuten
wandelen	fietsen		wandelen	fietsen
2 minuten	2 minuten	Steep ramp test	2 minuten	2 minuten
traplopen	traplopen		traplopen	traplopen
1 minuut	1 minuut	HIIT	1 minuut	1 minuut
opstaan-zitten-	opstaan-zitten-		opstaan-zitten-	opstaan-zitten-
opstaan	opstaan		opstaan	opstaan

Table: example of a weekly training program

Thuis (4x per week): vaste tijd (bvb. 9u – 10u) overeengekomen met de fysiotherapeut.
Van tevoren zuurstofsaturatie, pols, RR en aantal sigaretten via de Luscii app
Op basis van CPET:

- 10 / 20 / 30 minuten per dag matig-intensief actief zijn (thuis, mensen merken dat ze meer moet ademhalen):
 - Wandelen
 - o Fietsen
- 1 / 2 / 5 minuten hoog-intensief (thuis):
 - Traplopen
 - o Opstaan uit de stoel en weer gaan zitten.

Na de training wederom O2, pols, RR via de Luscii app doorsturen.

Één keer per week fysiotherapie

[figure not shown]
Van tevoren zuurstofsaturatie, pols, RR en aantal sigaretten via de Luscii app Op basis van aangepaste steep ramp test (10 W /10 s):

Nadat de aangepaste SRT op baseline is uitgevoerd (Figuur 1, Grafieken A en C), kan het (gedeeltelijk) gesuperviseerde trainingsprogramma, bestaande uit 3 HIIT-sessies van 25 minuten per week, worden uitgevoerd in de leefomgeving van de patiënt (in de eerste lijn of thuis).

- Elke trainingssessie bestaat uit een warming-up van 3 minuten op een belasting van 20 W, gevolgd door 14 arbeidsintervallen van 30 seconden op een hoge intensiteit van 60% van de SRT Wpiek
- Afgewisseld met 14 herstelintervallen van 60 sec op een lage intensiteit van 20 W

 Waarna een cooling-down van 1 minuut volgt op een belasting van 20 W (Figuur 1, grafieken B en C).

De trainingsintensiteit tijdens de arbeidsintervallen met hoge intensiteit komt overeen met ongeveer 90% van de CPET Wpiek. De aangepaste SRT dient wekelijks of tweewekelijks herhaalt te worden om veranderingen in de cardiorespiratoire fitheid te monitoren, terwijl het programma dienovereenkomstig kan worden aangepast om een adequate trainingsprikkel te behouden.

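### Three feasibility rates are defined as ratios of one patient group to the other, so drop-out as defined cannot be compared with the planned 20%, and adherence as defined contains no session information

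*Protocol*

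**What the plan says.** The Objectives section, under Other Secondary Objective(s), defines five feasibility rates:

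- Recruitment: "recruitment rate (how many patients will consent to participate in relation to the patients refusing participation".
- Adherence: "how many patients will endure participation in relation to the patients who give up participation, a.k.a. dropout rate", with a pointer to Appendix 1, a day-by-day training log.
- Completion: completers set against patients ending participation.
- Drop-out: "drop-out rate (how many patients will drop out of participation in relation to the number of patients completing participation".
- Attrition: how many patients ask about moving to another facility, with no denominator.

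Section 8.2 says that feasibility, including adherence or compliance, will be summarised descriptively. It does not redefine the rates.

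Elsewhere the denominator is different. Section 2.4 plans 100 inclusions, "assuming an exclusion rate of 20%, and a drop-out rate of 20" per cent. Section 6.7 ties early termination to withdrawal of more than half of the included subjects.

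On the number of sessions, section 1 gives five a week including the physical therapist, and states "Four times a week subjects perform exercises at home". Section 3.1 says "The treatment consists of a daily training at home during weekdays", with a weekly therapist session besides. Appendix 2 also describes a programme "bestaande uit 3 HIIT-sessies van 25 minuten per week".

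**The concern.** A rate is normally read as a share of a named group. Here recruitment, drop-out and adherence each divide one group by the other. The result is larger than the corresponding proportion and can exceed 100%. A reader who compares the reported drop-out with the 20% planned in section 2.4 would conclude that the trial lost more patients than foreseen, even if it lost exactly the planned number.

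Adherence is the more substantive problem. As defined, it counts patients who stay and carries no information about sessions. The Introduction names the number of prescribed sessions as a likely factor in improvement and says that these rates will be evaluated in relation to patient characteristics. A retention ratio cannot show whether patients who did not improve had actually trained.

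**Working it through.** **Inputs.** Section 2.4: 60 evaluable patients required, 100 to include, 20% exclusion, 20% drop-out. Objectives: the definitions above. Section 6.7: withdrawal counted against included subjects.

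**Step 1: reproduce the planned number.**

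- Both losses as shares of those included: 60/(1 − 0.20 − 0.20) = 60/0.60 = 100. This matches exactly.
- Drop-out applied only to those left after exclusion: 60/(0.80 × 0.80) = 93.75, so 94. No match.
- Inflating by the percentages: 60 × 1.4 = 84, or 60 × 1.2 × 1.2 = 86.4. No match.
- Reading the 20% as the ratio in the Objectives: the proportion is 0.20/1.20 = 16.7%, giving 60/(1 − 0.20 − 0.167) = 94.7, so 95, or 60/(0.80 × 0.833) = 90. No match.

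So section 2.4 uses drop-out as a proportion of included patients. Its scenario is 100 included, 20 excluded, 80 starting training, 20 drop-outs and 60 completers.

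**Step 2: apply the definitions in the Objectives to that scenario.**

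| Quantity | As defined | As a proportion |
|---|---|---|
| Drop-out | 20/60 = 33% | 20/100 = 20% of included; 20/80 = 25% of starters |
| Adherence (retention) | 60/20 = 300% | 60/80 = 75% of starters |
| Completion, if those ending are all starters | 60/80 = 75% | 75% of starters |
| Completion, if those ending are the ones who stop early | 60/20 = 300% | 75% of starters |

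The adherence figure is the reciprocal of the drop-out figure: 60/20 = 1/(20/60). The two bullets report the same information twice.

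**Step 3: general size.** For a drop-out proportion d among starters, the defined rate is d/(1 − d):

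- 10% is reported as 11%
- 20% as 25%
- 30% as 43%
- 50% as 100%

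Recruitment behaves in the same way. The protocol gives no consent figure; assuming consent of 50%, 60%, 70% or 80% of those asked, the defined rate is 100%, 150%, 233% or 400%.

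**Step 4: the denominator that session adherence would need.**

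- Section 1, Table 3 in section 6.3 (daily home training on four days a week, plus one therapist visit), the Appendix 1 log and the example week in Appendix 2 agree on four home sessions plus one with the therapist.
- Section 3.1 has home training daily on weekdays, with the therapist session in addition.
- The running text of Appendix 2 has three high-intensity interval sessions a week.

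**The case against.** The case on the other side is substantial.

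- **Secondary and descriptive.** No hypothesis test or stopping rule uses these ratios, and section 6.7 already has its own denominator. This stands. A reader might infer that feasibility is a main deliverable that will size a later trial. The text does not say so: feasibility is listed among other secondary aims, and section 7.5 mentions a larger trial only in connection with safety monitoring.
- **Nothing is lost.** A ratio r converts to a proportion by r/(1 + r). This stands if counts are reported. In the planned scenario, though, 0.333/1.333 = 25%, which is the share of starters. The planning figure of 20% still needs the number included.
- **Left to an analysis plan.** Exact denominators and intervals often are. But here the protocol does state denominators, and they exclude the numerator group.
- **Adherence is not equated with drop-out.** The alias in the adherence bullet can attach to the patients who give up, and drop-out has its own bullet. That reading is possible, so the documents do not firmly support saying that the two are declared identical. Either way the bullet counts patients, not sessions.
- **The schedule is clear enough.** A reader might infer that four home sessions score only 80% against section 3.1. Table 3 weakens this, because it puts the daily home training on four days a week. The wording in section 3.1 and the three sessions in Appendix 2 still have to be reconciled with the rest.
- **The mismatch could be put at 25%.** That figure takes 64 completers of 80 starters, 16/64. It rests on sequential losses, which do not reproduce the 100 exactly. The reading that does gives 33%.

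**Conclusion.** The point holds as a defect in stated definitions. Recruitment, drop-out and adherence are odds presented as rates; completion is ambiguous; attrition has no denominator. With the trial running exactly to plan, drop-out would be reported as 33% against a planned 20%, and adherence as 300%. This rests on taking the definitions literally and on the reading of section 2.4 that reproduces its 100. On the sequential reading the gap is smaller (25% against 20%) but does not close.

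The primary analysis and the sample size are not affected, and published counts would allow the drop-out and recruitment ratios to be converted. Conversion does not repair adherence, because no session count enters its definition. The sponsor should correct this; it does not threaten the trial's main conclusion.

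**What to change.** Reword the definitions in the Objectives, and refer to them in section 8.2:

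- Recruitment = consented / eligible patients approached.
- Exclusion = judged unfit for training / included.
- Drop-out = dropped out / included, so that it is comparable with sections 2.4 and 6.7. Report dropped out / started training alongside. The second form alone would give 20/80 = 25% in the planned scenario and would still not match the planned 20%.
- Completion = completed the programme / started training. Report separately how many had the second CPET, so that a patient who trained but missed the test is not counted as a drop-out.
- Adherence = sessions performed / sessions prescribed over the patient's own training weeks, from the app and the Appendix 1 log.
- Delete the drop-out alias from the adherence bullet.
- Transfer requests = a count and a proportion of included, reported separately.

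Reconcile the statements on weekly sessions in section 1, section 3.1, Table 3 and Appendices 1 and 2, so that the adherence denominator is fixed. Which schedule applies is for the sponsor to decide.

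The cost is mainly wording. The sessions are already logged, so no new patient assessment is needed.
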